## Protocol Synopsis

### *Brief Summary*

We will conduct a parallel-arm, double-blind individually randomized control trial (RCT) in 30 healthy older adults, where attentional control demands in working memory training will be systematically increased using engaging game-based simulations. There are three parallel arms. The first two arms use experimenter-designed simulation games, where participants will be trained on either predictable low attentional control (Arm 1: Low-C) or unpredictable high attentional control (Arm 2: High-C) working memory games. The third arm uses a commercially-available strategy video game requiring highest level of attentional control (Arm 3: High-C+), by adding multi-tasking to the unpredictable attentional shifts in working memory. In all three training arms, neural and cognitive changes in both near and far tasks will be examined immediately after the 8-week long intervention. Long-term cognitive changes will also be assessed at 6 months after completion of training. The far and near cognitive domains that will be examined in this RCT are episodic memory (the primary cognitive outcome, and a marker of early stages of AD) and executive control (the secondary cognitive outcome). We expect that the high attentional control training arms will greatly improve both primary and secondary cognitive outcomes in older adults not only immediately after the training, but also at the +6-month period. We also expect cognitive frailty to interact with the extent to which attentional control is trained.

Additionally, a single-session, baseline functional neuroimaging data-set will be collected in a control group of 18 younger adults. These younger adults will not undergo any training. High attentional control training arms (High-C and High-C+) are also expected to heighten compensatory brain activation in older adults after intervention, for both episodic memory (primary outcome) and executive control (secondary outcome) in-scanner tasks, paralleling the baseline activity of younger brains. These high attentional control training arms are also expected to positively impact brain structures that progressively decline with aging. The data from younger adults, our functional control group, will provide critical information about the brain regions activated in young, healthy brains during episodic memory (far transfer) and executive functions (near transfer). It will also help us determine whether older adults' brain activity following training resembles that of younger brains.

The primary objectives of this double-blind RCT are to evaluate the efficacy of high attentional control training on episodic memory (primary cognitive outcome) in an older adult population, by evaluating a) immediate training-related

changes in performance and neural activation during episodic memory tasks, and b) long-term changes at a +6-month retention period in performance during episodic memory tasks. The secondary objective of this RCT is to evaluate the efficacy of high attentional control training on executive functions (secondary cognitive outcome) in an older adult population by evaluating neuro-cognitive changes in executive functions immediately after the training, and cognitive gains at +6-month retention period.

In order to achieve these objectives, cognitive measures of both primary and secondary outcomes will be collected in healthy older adults at before training (baseline), immediately after 8 weeks of training (immediate post-training), and 6 months after training completion. MRI scanning, including fMRI tasks of episodic memory (primary outcome) and executive functions (secondary outcome), will be conducted at baseline and at immediate post-training for older adults, and only once in younger adults.

### ***Study timeline for Year 1***

The first quarter of year 1 (that is, 0-3 months after the notice of the award) will include a study preparation phase, where we will finalize the study protocol, acquire and set-up the testing computers, tablets and licensed neurocognitive tests, advertise to recruit young and old participants, hire required personnel, and test the final versions of the games and the neurocognitive computerized tasks on the newly acquired computers and set up data safety protocols. In addition, data collection on 25 younger adults (the functional control group) and 26 older adults (10 Low-C; 10 High-C; 6 High-C+) will be completed within during this first year. This will provide us with some pilot data by the end of year 1 to establish that the clinical trial can be successfully conducted, and identify age-related differences in brain functions during the near and far transfer tasks by comparing baseline fMRI data of older adults to that of younger adults.

Recruitment and enrollment of older adults for the clinical trial will begin in the third quarter of year 1 (that is, 6 months after notice of the award), after the clinical trial has been registered with [clinicaltrials.gov](https://clinicaltrials.gov).

### **Study Design**

**Overview.** This parallel arm, individually randomized control trial (RCT) will recruit 34 older adults from Dallas and neighboring counties. We aim to retain at least 30 participants on whom immediate post-training gains in both *near* and *far* abilities can be observed. This RCT shall be registered at [ClinicalTrials.gov](https://clinicaltrials.gov). There will be a Clinical Coordination Team (co-directed by [name] and the Project Manager) that will implement the intervention and check in with the participants on a weekly basis regarding their training progress. A blinded data collection team, directed by a post-doctoral fellow, will collect both behavioral and neuroimaging assessments before and after training. There will also be

a Data Coordination Team (co-directed by [name] and a post-doctoral fellow) that will be responsible for scoring and preprocessing the data. All data will be deposited in a HIPAA compliant server at the PI's laboratory. The team leaders will meet twice a month and each team will meet weekly to oversee any issues with subject recruitment, logistics and data collection. We will also recruit a total of 20 younger adults (YA, 18-30 years of age) for neuroimaging, who will be the functional controls for the older adults in the RCT.

This is a Phase 1 trial with multiple interventions in older adults, where the goal is to compare high attentional control trainings (High-C and High-C+) to low attentional control training (Low-C) and evaluate training-related changes in neurocognitive functions of both near (secondary outcome) and far transfer (primary outcome) tasks.

***Experimental Design.*** There are three intervention arms for older adults (OA) in this RCT trial, where attentional control demands in working memory training will be systematically increased using engaging game-based simulations.

Arm 1: Low Attentional Control Group (Low-C). Low attentional control training using an n-back simulation game (*Birdwatch*), requiring predictable shifts of cued-attention. Arm 2: High Attentional Control Group (High-C). High attentional control training using the *Birdwatch* simulation game, requiring unpredictable shifts of cued-attention. Arm 3: Highest Attentional Control Group (High-C+). This arm uses a commercial strategy video game for training (*Sushi Chef*), rather than the experimenter-developed simulation games proposed in the other two arms. Additionally, a *comparison group of younger adults (YA)* will undergo pre-screening, mock scan, and MRI scan sessions (but no training). All older participants will undergo 3 behavioral assessment sessions, each lasting a maximum of 3.5 hours, in the PI's lab. These assessments will be conducted at baseline, immediately post-training and 6 months after completion of training. All older adults will also undergo 2 neuroimaging assessments, one at baseline, and another at immediate post-training. There will no more than 5-day difference between the MRI scan and the respective behavioral assessment at either baseline or at immediate post-training.

The training period will last for 19 h over 8 weeks, and will include both in-lab and at-home training on a device provided to the participant. All training will be administered individually to the participant, not in a group. Fig. 5 and Fig. 6 show the computerized games used in the three training arms.

***Screening and Randomization.*** In this individually randomized trial, all interested participants will first be prescreened and will undergo a Mock Scan session to determine their eligibility to participate in the study. Participants will be consented to screening for eligibility. In order to exclude participants with memory-related disorders, primarily MCI and AD, participants will be required to have both a Mini-mental Status Examination (MMSE) score of 26 or greater, and a

Montreal Cognitive Assessment (MoCA) score of 24 or greater. A composite of these two standardized scores will comprise an index of *cognitive frailty*. The cutoff scores are conservative and should screen out most cases of MCI, although we acknowledge that some early stage MCI individuals could still be included. Additionally, brain scans will be screened by a neuroradiologist if a pathology is suspected.

If after the pre-screening and the Mock Scan sessions, a volunteer meets the inclusion and exclusion criteria, he or she will be randomized into one of the three training arms. This assignment will be based on a random computerized allocation plan, where the average cognitive frailty, age, education and gender distribution will be maintained to be equivalent across the three arms. By randomly assigning participants in the training arms and by assessing outcomes by blinded experimenters, we will avoid selection bias and outcome assessment bias. The power analyses for sample size justification, therefore, is for this individual randomized trial, where Type 1 and type II errors are defined, expected meaning difference between the experimental groups and Low-C are specified, and attrition is estimated at follow ups. The participant will need to be randomized to a training arm prior to any baseline assessments.

***Minimizing Attrition and Enhancing Adherence.*** Attrition at follow ups will be minimized because in addition to the weekly in-lab training, there will be weekly at-home training where the participants can conduct the training from the comfort of their home during their preferred time on the device (Windows tablet) provided to them. Compliance for at-home sessions will be measured by the device's time stamp, which will be recorded every time the participant logs into the training program. Participants will also be provided with a diary to keep a log of their training schedule to enhance compliance. Moreover, participants will be encouraged to call researchers of the unblinded, training group with any questions about the game. The weekly in-lab testing will ensure that any difficulties participants may encounter during at-home training is resolved.

***Sample Size Justification for the older adults in the RCT.*** We estimated the power (using G\*power3.1) to detect the differences between the Training Arm (3) x Assessment (2) interaction on the primary cognitive outcome. *The current study is the first phase of a larger randomized controlled trial. We calculate our power for the full trial, but our requested sample size for this study is 51.* We will recruit 177 older adults with the aim to retain a total sample size of 144 older adults at immediate post-training with the expected attrition of 18%. We report two expected effect sizes of Cohen's *f* for our calculations. One,  $f=.35$ , the minimum effect size obtained across our 3 pilot studies. Another,  $f=.16$ , based on a meta-analysis on computer-based cognitive training in older adults. The proposed total sample size of 144 older adults will provide us with >93% power to detect the Training Arm (3: Low-C, High-C, High-C+) x Assessment

(A vs. B) interaction at  $f=.16$  and  $>98\%$  power to detect the interaction at  $f=.35$  on the primary cognitive outcome at  $p<.05$ . It will also provide  $>90\%$  power to detect a meaningful between-group difference ( $f=.35$ ) at immediate post-testing, after controlling for baseline cognition, at  $p<.05$ . At +6mo retention period (Assessment C), we expect to retain a total of 117 older adults, after the expected  $\sim 20\%$  attrition between Assessments B and C. This will provide us with  $>87\%$  power to detect the Training Arm (3: Low-C, High-C, High-C+) x Assessment (2: A vs. C) interaction at  $p<.05$  at  $f=.16$ . We will conduct 2 ANOVAs, one for primary and one for secondary. Our proposed sample size will provide us with sufficient power ( $>87\%$ ) to detect the Training Arm (3) x Assessment (2) interaction at a corrected  $p$  value of .025 ( $=.05/2$  for 2 cognitive outcomes of interest).

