interest is the interaction between the Training Arms and Assessments. To evaluate the extent of immediate post-test cognitive gains across the three training arms, we will conduct pairwise contrasts between High-C and High-C+. Similar analysis will be conducted for the secondary outcome. The two ANOVAs will be adjusted to  $p < .025$  ( $= .05/2$ ) to adjust for multiple comparisons.

Additional analyses will investigate how *cognitive frailty*, as measured by MOCA and MMSE, interacts with training difficulty (High-C vs. High-C+) and extent of transfer, because cognitively fit older adults show faster learning rates for complex skills and working memory. We predict that older adults with greater cognitive frailty will exhibit less cognitive plasticity and therefore will benefit most from moderate attentional control training (High-C), whereas older adults with higher cognitive functioning will find the most challenging training dose (High-C+) to be most beneficial and exhibit greatest cognitive plasticity.

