**Fig. 4. An Illustration of Data Collection Timeline**

**a**

**b**

**Fig. 5. (a)** Trials from the Low-C Bird Watch game, where order of trees is predictable and the number of trees increase adaptively with the player's success. At the end of each game, feedback is provided. **(b)** A trial from the High-C Bird Watch game, where the order of the trees is unpredictable. Also, as shown, in some events when the trees change into fall color, the bird should be ignored for subsequent comparison.

**Fig. 6.** Screenshot of Sushi Chef simulation game showing day (i.e. level).

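### High-C+ changes the game as well as the control demand, so no contrast with High-C+ isolates attentional control, yet the only pairwise cognitive contrast named involves it

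*Combined protocol and SAP*

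**What the plan says.** Study Design (Experimental Design) defines the arms as follows.

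- Arm 1, Low-C: "Low attentional control training using an n-back simulation game (*Birdwatch*), requiring predictable shifts of cued-attention".
- Arm 2, High-C: "High attentional control training using the *Birdwatch* simulation game, requiring unpredictable shifts of cued-attention".
- Arm 3, High-C+: a commercial strategy game, Sushi Chef, "rather than the experimenter-developed simulation games proposed in the other two arms".

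The Brief Summary presents the three arms as one graded factor, "where attentional control demands in working memory training will be systematically increased using engaging game-based simulations", and describes the third as reaching the highest level "by adding multi-tasking to the unpredictable attentional shifts in working memory".

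The Data Analysis Plan fits a Training Arm (3) x Assessment (2) ANOVA. For the cognitive composites, the only pairwise follow-up it names is High-C against High-C+. The frailty analysis treats that same pair as a difference in training difficulty, describes High-C as moderate training, and predicts that higher-functioning participants "will find the most challenging training dose (High-C+) to be most beneficial".

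For imaging, the comparison with younger adults uses post-test Low-C, post-test High-C+ and the younger group, and leaves High-C out. The connectivity analysis compares High-C with High-C+ to see whether the latter produces the most neural change.

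**The concern.** The scientific question is what happens as attentional control demand rises. Answering it requires arms that differ in control demand with the rest of the training held fixed. High-C vs Low-C comes close to that. High-C+ does not: moving to it changes the control demand and the game together.

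If High-C+ does better or worse than High-C, the plan as worded would read the result as an effect of more attentional control, or of greater difficulty. The same result could come from the change of game. The cognitive follow-up, the frailty prediction and the comparison with younger adults all rely on the arm in which the two cannot be told apart. The plan nowhere matches the games on content, measures control load, includes a low-control version of Sushi Chef, or names the change of game as a limit on interpretation. Since the sample size section calls this the first phase of a larger trial, the reading would carry forward.

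**Working it through.** **1. What the three arms can identify.** Write the mean gain in each arm as:

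- Low-C: a
- High-C: a + c1 (added demand within Birdwatch)
- High-C+: a + c1 + c2 + g (c2 = further control demand, g = effect of changing the game)

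The contrasts are then:

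| Contrast | Expected difference | Same game? |
|---|---|---|
| High-C vs Low-C | c1 | yes |
| High-C+ vs High-C | c2 + g | no |
| High-C+ vs Low-C | c1 + c2 + g | no |

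There are three means and four unknowns, and c2 and g appear only as a sum. More participants estimate the sum more precisely but do not split it. Randomisation balances participants across arms, and the 19 h of training is stated once for all arms; neither alters this. No value is put on g, because the documents give none.

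**2. Which planned analyses depend on c2 + g.**

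- Cognitive pairwise follow-up (High-C vs High-C+): yes.
- Frailty by training difficulty (same pair): yes, for the interaction with frailty.
- Low-C / High-C+ / younger-adult ANOVA: yes; its older-adult difference is c1 + c2 + g.
- Connectivity, High-C vs High-C+: yes.
- Three-arm interaction: valid as a test of any arm difference, but it could be significant through g alone.
- Specific Aim 2 planned comparisons with Low-C: the High-C part is free of g; the High-C+ part is not.

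**3. Is High-C vs Low-C clean?** Cleaner, but not pure. The Fig. 5 caption describes Low-C as a game "where order of trees is predictable and the number of trees increase adaptively with the player's success". For High-C it adds a rule to ignore birds when trees turn to fall colour, and it does not say whether tree number adapts there. So c1 covers unpredictability plus the ignore rule. That rule may itself count as control demand, but it should be stated.

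**4. Power of the one same-game contrast.** Within-between interaction by noncentral F: lambda = f^2 x N x m / (1 - rho), with m = 2 assessments and df = (k - 1, N - k) for k arms. The plan gives no pre-post correlation; rho = .5 is assumed.

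The plan's own figures come first (Sample Size Justification, f=.16, alpha .05, k = 3):

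- N=144: lambda = .0256 x 144 x 2 / .5 = 14.75, df (2, 141), power 93.5%. Stated: above 93%. Reproduced. Range: 82.8% at rho .3 to 99.5% at rho .7.
- N=117: lambda = 11.98, df (2, 114), power 87.4%. Stated: above 87%. Reproduced.

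Next, High-C vs Low-C (k = 2), keeping the plan's f values by assumption. Study Design aims to retain at least 30; 30 / 3 = 10 per arm is assumed, so N = 20 and df = (1, 18). The Year 1 timeline also lists 10 Low-C and 10 High-C.

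| f | lambda (rho .5) | Power, alpha .05 | rho .3 to .7, alpha .05 | Power, alpha .025 (rho .5) |
|---|---|---|---|---|
| .16 | .0256 x 20 x 2 / .5 = 2.05 | 27% | 21% to 42% | 18% |
| .35 | .1225 x 20 x 2 / .5 = 9.80 | 84% | 71% to 97% | 75% |

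At the full-trial size, 144 x 2/3 = 96 in the two arms, f=.16 and rho .5 give 87% (alpha .05) or 80% (alpha .025).

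**The case against.** The change of game is disclosed, in both the Brief Summary and Study Design, and a reason is given for it. The trial is described as having multiple interventions, and a commercial-game arm has practical value of its own. This stands, and nothing here asks for the arm to be dropped. Disclosure is not the same as limiting the conclusion, though, and the plan does not do the latter.

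The word dose occurs once, in a prediction. Training Arm is a three-level categorical factor throughout, with no trend test or ordinal coding. This also stands. A reader might infer that the plan fits a dose-response model, or that its ANOVA is invalid; the documents support neither. The tests remain sound randomised comparisons of training packages.

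A reader might also infer that the plan never sets High-C against Low-C. It does: Study Design states the goal as comparing both high-control trainings with Low-C, and Specific Aim 2 includes comparisons between the groups. What is missing is that pair as a named contrast on the cognitive composites. The connectivity question is likewise worded about the arm, and does not by itself credit attentional control.

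Finally, a reader might suppose that Sushi Chef wins by being richer or more engaging. The documents describe all the games as engaging and say little about how Sushi Chef plays, so that explanation has no basis in them. Overlap with training is a more concrete possibility, since two of the six executive tasks are n-back. It touches only the secondary outcome and the n-back fMRI task: none of the four episodic memory tests is n-back, and the plan regards updating as near transfer for all arms.

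**Conclusion.** The point holds as a limit on attribution. Two of the three pairwise contrasts, including the only one named for the cognitive outcomes, change the game together with the control demand, so neither can be credited to attentional control alone. This follows from the arm definitions and depends on no numerical assumption. It does not show that the game has an effect, nor how large one would be.

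High-C vs Low-C is the best available basis for a conclusion about attentional control, subject to the ignore rule in Fig. 5. In this phase it is weak at the plan's smaller effect size and fair at its larger one. The power figures rest on 10 retained per arm, the correlation range shown, and the plan's f carried over unchanged to two arms.

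**What to change.** In the Data Analysis Plan, cognitive outcomes:

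- Add High-C vs Low-C as a named pairwise contrast on both composites.
- State that, as the only same-game comparison, it is the basis for conclusions about attentional control, and that High-C also includes the ignore rule.
- Report High-C+ vs High-C, High-C+ vs Low-C and the frailty-by-arm analysis as comparisons of training packages, without describing the difference as one of dose or training difficulty.

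In the neuroimaging section, apply the same package wording to the Low-C / High-C+ / younger-adult ANOVA and to the High-C vs High-C+ comparisons.

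This needs no new data, visits or participants. It costs a narrower claim for the third arm and one added contrast. The report should also acknowledge that a null High-C vs Low-C result from about 20 participants would say little about an effect near f=.16.

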### **Data Analysis Plan**

All data will be initially tested for normality, outliers, and errors. We will then compute summary statistics and derive across-group statistical comparisons to identify any demographic variables, such as age, gender, education, or cognitive frailty, group differences after the randomization process. If group differences are detected for a variable, all analyses will include that variable as a covariate. We will also present primary and secondary outcome measures using descriptive statistics, summarize categorical variables using frequencies and proportions, and report descriptive statistics as medians and interquartile ranges.

***Analyses of Primary and Secondary Cognitive Outcomes.*** Outcomes will be tested according to the intention-to-treat principle with analysis of variance, evaluating both the changes from baseline to the completion of training (immediate treatment effects) and the changes from baseline to +6mo after training (retention effects). All analyses will be conducted on the baseline-normed Blom transformed scores for each measure, an approach used in prior intervention research on older adults. Composite cognitive scores (for each cognitive outcome) will be formed by averaging these scores. Therefore, we shall conduct all statistical analyses on one composite cognitive score representing the primary outcome (episodic memory) and one composite score representing the secondary outcome. There will be, for both outcomes, three composite scores- one for each Assessment (A, B and C). Specific Aim 1 focuses on the increases in cognition between the three training arms at both immediate post-testing and +6mo period. Change scores for each composite score for each individual will first be plotted to evaluate the treatment-related cognitive benefits. We will then examine the composite scores for the primary outcome using repeated measures ANOVA, with Training Arms (3: Low-C, High-C, High-C+) as a between-subject factor and Assessment (2) as a within-subject factor, for both immediate post-training gains (Assessments A and B) and for long-term retention of these gains (Assessments A and C). Of main

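### Randomising before Assessment A, for no stated reason, allows participants to be randomised and then lost without a baseline, and leaves open arm knowledge at baseline

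*Combined protocol and SAP*

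**What the plan says.** The Screening and Randomization paragraph of Study Design first places randomisation after eligibility: "If after the pre-screening and the Mock Scan sessions, a volunteer meets the inclusion and exclusion criteria, he or she will be randomized" to one of three arms. It closes with a further rule on timing: "The participant will need to be randomized to a training arm prior to any baseline assessments". No reason is given for that rule.

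The method is brief: "This assignment will be based on a random computerized allocation plan", balanced on cognitive frailty, age, education and gender. Frailty comes from the MMSE and MoCA, which are eligibility scores: "A composite of these two standardized scores will comprise an index of" cognitive frailty. The same paragraph adds that "brain scans will be screened by a neuroradiologist if a pathology is suspected". Only a mock scan precedes randomisation, and the first real scan described for older adults is the baseline MRI.

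On blinding, the Overview says that a blinded team "will collect both behavioral and neuroimaging assessments before and after training". The adherence paragraph mentions a separate unblinded group: "participants will be encouraged to call researchers of the unblinded, training group with any questions about the game".

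The Data Analysis Plan states: "Outcomes will be tested according to the intention-to-treat principle". The analysis it then specifies is a repeated-measures ANOVA of arm by assessment on baseline-normed composite scores, once for A and B and once for A and C.

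**The concern.** A full baseline is not a formality in this trial. It consists of a behavioural session of up to 3.5 hours and an MRI up to five days apart from it. Refusal, a failed scan or withdrawal can occur in that window. Under the stated order, each such case is a randomised participant.

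Two things are at stake. First, a randomised participant without Assessment A is outside both cognitive analyses, so the analysed set is no longer everyone who was randomised. Second, if a participant already knows the arm, that knowledge could affect baseline effort or the decision to attend. Losses or baseline scores could then differ by arm. The documents do not describe how or when the arm is disclosed to the participant, so this cannot be excluded.

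**Working it through.** **1. Does anything require this order?** The four balancing factors are frailty (MMSE and MoCA, obtained to decide eligibility), age, education and gender. None depends on Assessment A or on the baseline MRI.

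**2. Which analyses need a baseline?** Both cognitive ANOVAs (A with B, A with C) do, and so does the arm-by-assessment ANOVA for the fMRI outcome. The post-test comparison mentioned in the sample size paragraph adjusts for baseline cognition. Of the main analyses, only the post-test imaging comparisons could use someone without a baseline. Attrition is discussed only at follow-ups, and no rule covers a missing Assessment A.

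**3. Reproducing the plan's own figures.** For the within-between interaction I used a noncentral F with λ = f²·N·m/(1 − ρ), m = 2 assessments, k = 3 arms, df = 2 and N − 3. The correlation ρ is not stated; 0.5 is assumed.

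- N = 144, f = .16, α = .05: λ = 0.0256 × 144 × 2 / 0.5 = 14.75, power 93.5% (stated: above 93%).
- N = 117: λ = 0.0256 × 117 × 2 / 0.5 = 11.98, power 87.4% (stated: above 87%).
- Recruitment: 144 / (1 − 0.18) = 175.6, so 176 (stated: 177).

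The figures reproduce at ρ = 0.5. For ρ from 0.3 to 0.7, power runs from 82.8% to 99.5% at N = 144 and from 73.6% to 98.3% at N = 117.

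**4. Size of the pre-baseline loss.** The documents give no rate. I assumed 2%, 5% and 10% and applied these to the 34 to be recruited in this phase (Study Design, Overview) and to the 177 of the full trial. The loss is taken on top of planned attrition, so the number with both A and B is 30 × (1 − q) or 144 × (1 − q), rounded. Power is at α = .05 and ρ = 0.5.

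| Assumed loss q | Lost of 34 | N with A and B | Power, f = .35 | Power, f = .16 | Lost of 177 | N with A and B | Power, f = .16 |
|---|---|---|---|---|---|---|---|
| 0% | 0 | 30 | 91.1% | 29.8% | 0 | 144 | 93.5% |
| 2% | 0.7 | 29 | 89.9% | 28.8% | 3.5 | 141 | 93.0% |
| 5% | 1.7 | 28 | 88.7% | 27.8% | 8.8 | 137 | 92.3% |
| 10% | 3.4 | 27 | 87.3% | 26.8% | 17.7 | 130 | 90.8% |

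**5. Against the plan's allowance.** Recruiting 34 to retain 30 allows 34 − 30 = 4 losses up to immediate post-training. A pre-baseline loss of 0.7 to 3.4 would use 0.68/4 = 17% to 3.4/4 = 85% of that allowance before training begins. With equal arms of 34/3 = 11.3, an even spread is 0.2 to 1.1 people per arm.

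**The case against.** The strongest reply is that most of the incomplete-data problem has nothing to do with timing. Repeated-measures ANOVA also drops anyone without B or C, and the plan expects 18% and then about 20% attrition. Moving randomisation leaves that untouched. This stands. But loss before baseline is the one part that design can remove completely. Someone who leaves at that point would usually have no outcome data at all, so a better missing-data model has little to work with beyond the screening scores.

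It is also fair to say that the trial is described as double-blind, that blinded assessors collect the pre-training data, and that the losses may be few. If nobody knows the arm, early drop-out cannot be driven by it and costs only precision. The risk of bias is therefore possible, not shown.

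Several stronger readings are tempting and should not be drawn:

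- *Allocation concealment is weakened.* Concealment means hiding the next assignment until the participant is enrolled. Here assignment follows confirmed eligibility, so a later baseline visit does not weaken it. That no concealment mechanism is described is a separate gap, whatever the timing.
- *Unblinded training staff know the arm before baseline testing.* The documents say only that such staff take calls about the game. They do not say when those staff learn the assignment, and those staff are not the assessors.
- *Participants will be excluded on the baseline scan.* The text provides for a neuroradiologist's read on suspicion. It neither states nor rules out exclusion afterwards.
- *Up to a third of an arm could be lost.* This puts the whole upper bound in one arm (3.4/11.3 = 30%). If three people are lost independently of arm, with equal arms, the chance that all fall in the same arm is 3 × (1/3)³ = 1/9.

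**Conclusion.** The point holds in limited form. The plan fixes an order that it does not justify and that its own balancing factors do not require. That order allows randomised participants to have no baseline, and the specified ANOVA cannot include them, contrary to the stated intention-to-treat principle. It also leaves participants' knowledge of their arm at baseline unaddressed.

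The order permits such losses; nothing shows that they will occur, or at what rate. The count of 0.7 to 3.4 of 34 rests entirely on the assumed 2% to 10%. The power figures rest also on ρ = 0.5 and on the loss being additional to planned attrition. On those assumptions power falls by at most 3.8 percentage points in this phase (91.1 − 87.3) and 2.7 in the full trial (93.5 − 90.8). Power is not the reason to act. The reasons are a clean intention-to-treat set and baseline scores that cannot have been influenced by assignment. The change is worth making because it is cheap, and it carries over to the larger trial.

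**What to change.** Replace the sentence on timing with one to this effect: *Participants will be randomised after the behavioural and MRI parts of Assessment A are complete and eligibility has been confirmed, immediately before the first training session.* The same four balancing factors can be used unchanged. The protocol should also say whether a finding on the baseline scan bears on eligibility, so that it is clear what confirmation of eligibility covers.

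The cost is one sentence and slightly later scheduling of training. No stated sample size or power figure changes.

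If the present order has to stay, the protocol should give the reason, withhold the arm from the participant until baseline is complete, and state how the intention-to-treat analysis treats a randomised participant with no Assessment A. That would deal with the bias and the definition of the analysis set, but would not prevent the loss.
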